4.3.3.1 Management Algorithms for Immuno-Oncology Agents

Immuno-oncology (I-O) agents are associated with adverse events that can differ in severity and duration than adverse events caused by other therapeutic classes. Nivolumab, ipilimumab, BMS-986016, and daratumumab are considered immuno-oncology agents in this protocol. Early recognition and management of adverse events associated with immuno-oncology agents may mitigate severe toxicity. Management algorithms have been developed to assist investigators in assessing and managing the following groups of adverse events:

- Gastrointestinal
- Renal
- Pulmonary

- Hepatic
- Endocrinopathies
- Skin
- Neurological
- Myocarditis

While the ipilimumab investigator brochure contains safety management algorithms for similar adverse events, the recommendations are to follow the nivolumab algorithms for immuno-oncology agents (I-O) in order to standardize the safety management. Therefore, the algorithms recommended for utilization in this protocol are included in Appendix 1.

For subjects expected to require more than 4 weeks of corticosteroids or other immunosuppressants to manage an adverse event, consider recommendations provided in Appendix 1.

4.3.4 Dose Modifications

There will be no dose reductions for nivolumab, ipilimumab, BMS-986016 or daratumumab.

4.3.5 Criteria to Resume Treatment

Subjects may resume treatment with study drug when the drug-related AE(s) resolve to Grade ≤ 1 or baseline value, with the following exceptions:

- Subjects may resume treatment in the presence of Grade 2 fatigue
- Subjects who have not experienced a Grade 3 drug-related skin AE may resume treatment in the presence of Grade 2 skin toxicity
- Subjects with baseline Grade 1 AST/ALT or total bilirubin who require dose delays for reasons other than a 2-grade shift in AST/ALT or total bilirubin may resume treatment in the presence of Grade 2 AST/ALT OR total bilirubin. Subjects with combined Grade 2 AST/ALT AND total bilirubin values meeting discontinuation parameters (Section 4.3.6) should have treatment permanently discontinued
- Drug-related pulmonary toxicity, diarrhea, or colitis, must have resolved to baseline before treatment is resumed
- Drug-related endocrinopathies adequately controlled with only physiologic hormone replacement may resume treatment
- Subjects in the C5 Cohort may resume treatment with BMS-986016 when troponin levels return to normal

In the case of prior SARS-CoV-2 infection, symptoms should have resolved in order to resume study treatment and there should be no sequelae that would place the participant at a higher risk of receiving study intervention.

If the criteria to resume treatment are met, the subject should restart treatment at the next scheduled time point per protocol. However, if the treatment is delayed past the scheduled time point per protocol, the scheduled study treatment administration will be delayed, but not skipped, until

dosing resumes. In particular, this is to ensure that subjects in Arm N+I will receive 4 administrations of combined nivolumab and ipilimumab treatment if toxicity allows.

If dose delay is necessary for subjects in Arm N+I during Week 1-12 and for subjects in Cohort C3, both nivolumab and ipilimumab must be delayed until treatment can resume. However, if a nivolumab-related infusion reaction prevents subsequent infusion of ipilimumab on the same day, the dose of ipilimumab should be replaced as soon as possible. In such instances, at least 19 days must elapse between the replacement dose of ipilimumab and the administration of the next dose of nivolumab combined with ipilimumab.

If treatment is delayed > 6 weeks from the last dose, the subject must be permanently discontinued from study therapy, except as specified in Section 4.3.6.

Subjects may resume treatment with daratumumab in Cohort 6, upon recovery from toxicity to Grade 2 or baseline, with the exception that Grade 2 laryngeal edema or Grade 2 bronchospasm must be fully recovered. If the daratumumab administration does not commence within the pre-specified window of the scheduled administration date, then the dose will be considered a missed dose. Administration may resume at the next planned dosing date.

4.3.6 Discontinuation Criteria

Treatment with nivolumab, ipilimumab, and/or BMS-986016 should be permanently discontinued for the following:

- Any Grade 2 drug-related uveitis or eye pain or blurred vision that does not respond to topical therapy and does not improve to Grade 1 severity within the re-treatment period OR requires systemic treatment
- Any Grade 3 non-skin, drug-related adverse event lasting > 7 days, with the following exceptions for drug-related laboratory abnormalities, endocrinopathies, uveitis, pneumonitis, bronchospasm, diarrhea, colitis, neurologic toxicity, hypersensitivity reactions, and infusion reactions:
 - Grade 3 drug-related uveitis, pneumonitis, bronchospasm, diarrhea, colitis, neurologic toxicity, myocarditis, hypersensitivity reaction, or infusion reaction of any duration requires discontinuation
 - For Grade 3 endocrinopathy adverse events such as adrenal insufficiency, ACTH deficiency, hyper- or hypothyroidosis, or glucose intolerance, which resolve or are adequately controlled with physiologic hormone replacement (steroids, thyroid hormones) or glucose controlling agents, respectively, do not require treatment discontinuation
 - Grade 3 drug-related laboratory abnormalities do not require treatment discontinuation except:
 - ◆ Grade 3 drug-related thrombocytopenia > 7 days or associated with bleeding requires discontinuation
 - Any drug-related liver function test (LFT) abnormality that meets the following criteria require discontinuation:
 - \circ AST or ALT $> 8 \times ULN$

Protocol Amendment No: 09

Approved v1000 930073805 10.0

- o Total bilirubin > 5 x ULN
- o Concurrent AST or ALT > 3 x ULN and total bilirubin > 2 x ULN
- Any Grade 4 drug-related adverse event or laboratory abnormality (including but not limited to creatinine, AST, ALT, or Total Bilirubin), except for the following events which do not require discontinuation:
 - Grade 4 neutropenia \leq 7 days
 - Grade 4 lymphopenia or leukopenia
 - Grade 4 amylase or lipase abnormalities that are not associated with symptoms or clinical manifestations of pancreatitis.
 - Isolated Grade 4 electrolyte imbalances/abnormalities that are not associated with clinical sequelae and are corrected with supplementation/appropriate management within 72 hours of their onset
 - Grade 4 drug-related endocrinopathy adverse events, such as hyper- or hypothyroidism, or glucose intolerance, which resolve or are adequately controlled with physiologic hormone replacement (corticosteroids, thyroid hormones) or glucose-controlling agents, respectively, may not require discontinuation after discussion with and approval from the BMS Medical Monitor
- Any dosing interruption lasting > 6 weeks from the last dose with the following exceptions:
 - Dosing interruptions to allow for prolonged steroid tapers to manage drug-related adverse events are allowed. Prior to re-initiating treatment in a subject with a dosing interruption lasting > 6 weeks from the last dose, the BMS medical monitor/designee must be consulted. Tumor imaging assessments should continue as per protocol even if dosing is interrupted.
 - Dosing interruptions > 6 weeks from the last dose that occur for non-drug-related reasons may be allowed if approved by the BMS medical monitor/designee. Prior to re-initiating treatment in a subject with a dosing interruption lasting > 6 weeks from the last dose, the monitor/designee must be consulted. Tumor imaging assessments should continue as per protocol even if dosing is interrupted.

Any adverse event, laboratory abnormality, or intercurrent illness which, in the judgment of the Investigator, presents a substantial clinical risk to the subject with continued nivolumab, ipilimumab, and/or BMS-986016 dosing.

Daratumumab treatment should be permanently discontinued for the following reasons:

- Grade 4 infusion reactions related to daratumumab.
- For Grade 3 infusion reactions related to daratumumab: Once reaction symptoms resolve, consider restarting the infusion at no more than half the rate at which the reaction occurred. If the patient does not experience additional symptoms, resume infusion rate escalation at increments and intervals as outlined in Table 4.1.3.5-1. Repeat the procedure above in the event of recurrence of Grade 3 symptoms. Permanently discontinue daratumumab upon the third occurrence of a Grade 3 or greater infusion reaction.

Protocol Amendment No: 09

Approved v1000 930073805 10.0

Any adverse event, laboratory abnormality, or intercurrent illness which, in the judgment of the Investigator, presents a substantial clinical risk to the subject, regardless of cohort, with continued study drug dosing should discontinue the study drugs.

The consideration to re-initiate study therapy in selected cases at any time point after discontinuation could be made on a case-by-case basis after considering the overall benefit/risk profile and in consultation between the Investigator and the study Sponsor. The selected subjects will need to meet eligibility criteria. The original dose and schedule and protocol rules would apply accordingly (Section 4.3.6).

The assessment for discontinuation of study drug should be made separately considering each study drug component in the nivolumab and ipilimumab, and nivolumab and daratumumab (Cohort C6) combinations. If discontinuation criteria are attributed with only one drug used in this trial, once the subject meets criteria to resume therapy, the subject may continue dosing with nivolumab if nivolumab was not attributed to criteria for discontinuation.

In the nivolumab and BMS-986016 combination (Cohort C5), if discontinuation criteria are met, both drugs (nivolumab and BMS-986016) will be discontinued regardless of the assessment of attribution to a particular study drug.

If a subject meets criteria for discontinuation and the investigator is unable to determine whether the event is related to both or one study drug, the subject should discontinue all study drugs and be taken off the treatment phase of the study.

4.3.7 Treatment of Study Drug Related Infusion Reactions

Since nivolumab, ipilimumab, and BMS-986016 contain only human immunoglobulin protein sequences, it is unlikely to be immunogenic and induce infusion or hypersensitivity reactions. However, if such a reaction were to occur, it might manifest with fever, chills, rigors, headache, rash, pruritus, arthralgias, hypo- or hypertension, bronchospasm, or other symptoms. All Grade 3 or 4 infusion reactions should be reported within 24 hours to the BMS Medical Monitor and reported as an SAE if criteria are met. Infusion reactions should be graded according to NCI CTCAE (version 4.0) guidelines.

Treatment recommendations are provided below and may be modified based on local treatment standards and guidelines as appropriate:

For Grade 1 symptoms: (Mild reaction; infusion interruption not indicated; intervention not indicated)

Remain at bedside and monitor subject until recovery from symptoms. The following prophylactic premedications are recommended for future infusions: diphenhydramine 50 mg (or equivalent) and/or paracetamol 325 to 1000 mg (acetaminophen) at least 30 minutes before additional nivolumab administrations.

For Grade 2 symptoms: (Moderate reaction requires therapy or infusion interruption but responds promptly to symptomatic treatment [eg, antihistamines, non-steroidal anti-inflammatory drugs,

narcotics, corticosteroids, bronchodilators, IV fluids]; prophylactic medications indicated for ≤ 24 hours).

Stop the study drug infusion, begin an IV infusion of normal saline, and treat the subject with diphenhydramine 50 mg IV (or equivalent) and/or paracetamol 325 to 1000 mg (acetaminophen); remain at bedside and monitor subject until resolution of symptoms. Corticosteroid or bronchodilator therapy may also be administered as appropriate. If the infusion is interrupted, then restart the infusion at 50% of the original infusion rate when symptoms resolve; if no further complications ensue after 30 minutes, the rate may be increased to 100% of the original infusion rate. Monitor subject closely. If symptoms recur then no further study drug will be administered at that visit. Administer diphenhydramine 50 mg IV, and remain at bedside and monitor the subject until resolution of symptoms. The amount of study drug infused must be recorded on the electronic case report form (eCRF). The following prophylactic premedications are recommended for future infusions: diphenhydramine 50 mg (or equivalent) and/or paracetamol 325 to 1000 mg (acetaminophen) should be administered at least 30 minutes before additional study drug administrations. If necessary, corticosteroids (recommended dose: up to 25 mg of IV hydrocortisone or equivalent) may be used.

For Grade 3 or Grade 4 symptoms: (Severe reaction, Grade 3: prolonged [ie, not rapidly responsive to symptomatic medication and/or brief interruption of infusion]; recurrence of symptoms following initial improvement; hospitalization indicated for other clinical sequelae [eg, renal impairment, pulmonary infiltrates]). Grade 4: (life-threatening; pressor or ventilatory support indicated).

Immediately discontinue infusion of study drug. Begin an IV infusion of normal saline, and treat the subject as follows. Recommend bronchodilators, epinephrine 0.2 to 1 mg of a 1:1,000 solution for subcutaneous administration or 0.1 to 0.25 mg of a 1:10,000 solution injected slowly for IV administration, and/or diphenhydramine 50 mg IV with methylprednisolone 100 mg IV (or equivalent), as needed. Subject should be monitored until the investigator is comfortable that the symptoms will not recur. Study drug will be permanently discontinued. Investigators should follow their institutional guidelines for the treatment of anaphylaxis. Remain at bedside and monitor subject until recovery from symptoms. In the case of late-occurring hypersensitivity symptoms (eg, appearance of a localized or generalized pruritus within 1 week after treatment), symptomatic treatment may be given (eg, oral antihistamine, or corticosteroids).

Management of daratumumab infusion-related reactions

Subjects should be carefully observed during daratumumab infusions. Trained study staff at the clinic should be prepared to intervene in case of any infusion reactions, and resources necessary for resuscitation must be available. Attention to staffing should be considered when multiple subjects will be dosed at the same time.

For infusion reactions of any grade/severity, immediately interrupt the daratumumab infusion and manage symptoms. Management of infusion reactions may further require reduction in the rate of infusion, or treatment discontinuation of daratumumab.

Grade 1-2 (mild to moderate): Once reaction symptoms resolve, resume the infusion at no more than half the rate at which the reaction occurred. If the patient does not experience any further reaction symptoms, infusion rate escalation may resume at increments and intervals as appropriate as outlined in Table 4.1.3.5-1.

Grade 3 (severe): Once reaction symptoms resolve, consider restarting the infusion at no more than half the rate at which the reaction occurred. If the subject does not experience additional symptoms, resume infusion rate escalation at increments and intervals as outlined in Table 4.1.3.5-1. Repeat the procedure above in the event of recurrence of Grade 3 symptoms. Permanently discontinue daratumumab upon the third occurrence of a Grade 3 or greater infusion-related reaction.

Grade 4 (life threatening): Permanently discontinue daratumumab treatment.

4.3.8 Treatment Beyond Disease Progression

Accumulating evidence indicates a minority of subjects treated with immunotherapy may derive clinical benefit despite initial evidence of PD. ¹⁰⁶ The assessment of clinical benefit should take into account whether the subject is clinically deteriorating and unlikely to receive further benefit from continued treatment.

Subjects will be permitted to continue treatment for up to 24 months beyond initial RECIST 1.1 defined PD assessed by the investigator.

Subjects who progress following re-initiation of treatment have the option to be treated beyond progression for a cumulative maximum of 24 months from re-initiation dose.

All decisions to continue treatment beyond initial progression must be discussed with the BMS Medical Monitor and documented in the study records.

All subjects treated beyond progression must meet the criteria below:

- 1) Investigator-assessed clinical benefit, and do not have rapid disease progression
- 2) Tolerance of study drug
- 3) Stable performance status
- 4) Treatment beyond progression will not delay an imminent intervention to prevent serious complications of disease progression (eg, CNS metastases)
- 5) Subject provides written informed consent prior to receiving any additional nivolumab treatment, or nivolumab in combination with ipilimumab treatment, using an ICF describing any reasonably foreseeable risks or discomforts, or other alternative treatment options.

Treatment beyond progression may be administered during or after localized interventions (surgery/radiation therapy).

For subjects with time point response of progression being treated beyond progression, scans should be repeated every 12 weeks or earlier, as clinically indicated, to assess further disease progression.

Subjects will be re-consented with an ICF describing any reasonably foreseeable risks or discomforts. For subjects who have re-initiated treatment per Revised Protocol 07, treatment beyond progression will be according to the dose schedule during the re-initiation period.

Subjects should discontinue study therapy upon further evidence of further progression, defined as an additional 10% or greater increase with a minimum 5 mm absolute increase in tumor burden volume from time of initial progression (including all target lesions and new measurable lesions). Study treatment should be discontinued permanently upon documentation of further progression.

New lesions are considered measurable at the time of initial progression if the longest diameter is at least 10 mm (except for pathological lymph nodes, which must have a short axis of at least 15 mm). Any new lesion considered non-measurable at the time of initial progression may become measurable and therefore included in the tumor burden measurement if the longest diameter increases to at least 10 mm (except for pathological lymph nodes, which must have an increase in short axis to at least 15 mm). In situations where the relative increase in total tumor burden by 10% is solely due to inclusion of new lesions which become measurable, these new lesions must demonstrate an absolute increase of at least 5 mm.

For statistical analyses that include the investigator-assessed progression date, subjects who continue treatment beyond initial investigator-assessed, RECIST 1.1-defined progression will be considered to have investigator-assessed progressive disease at the time of the initial progression event.

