Section 4.3.8 Treatment Beyond Disease Progression	Added that subjects will be permitted to continue treatment for up to 24 months beyond initial RECIST 1.1 defined PD, as assessed by the investigator, and clarified that subjects who progress following reinitiation of treatment have the option to be treated beyond	For consistency with 24-month maximum treatment duration allowed for subjects who re-initiate treatmen and alignment with nivolumab essential

SUMMARY OF KEY CHAI	SUMMARY OF KEY CHANGES FOR PROTOCOL AMENDMENT 09			
Section Number & Title	Description of Change	Brief Rationale		
	progression for a cumulative maximum of 24 months from re-initiation dose.	protocol elements (EPE).		
	Added that treatment beyond progression may be administered during or after localized interventions.	Updated to clarify when treatment beyond progression may be administered.		
	Added "For subjects with time point response of progression being treated beyond progression, scans should be repeated every 12 weeks or earlier, as clinically indicated, to assess further disease progression."	To clarify that Investigator has flexibility to monitor progression with earlier scans if clinically indicated		
Section 4.3.9 Treatment Reinitiation Inclusion Criteria: MSI-H Cohorts	Added "Inclusion Criteria" to section title.	Added to clarify that the section lists inclusion criteria for subjects in order to re-initiate treatment.		
Section 5.1 Flow Chart/Time and Events Schedule	Removed "For MSI-H subjects only" and added "except for those enrolled in the non-MSI-H Safety Cohort" from EORTC QLQ-C30 and EQ-5D Questionnaires row of Table 5.1-2 and Table 5.1-3.	Fixing previous mistake.		
	Removed "through Week 23 visit and every alternate dose thereafter" from laboratory tests row of Table 5.1-2 and Table 5.1-3.	Every alternate dose was removed as planned sampling timelines are now aligned with dosing schedule.		
	Added troponin testing for Cohort C5 only in Table 5.1-7 and Table 5.1-13.	Consistency with relatlimab EPE.		
	Added "To Be Performed at Each Dosing Visit" to header in Table 5.1-9 and Table 5.1-10.	Added to clarify when assessments will be performed and for consistency across tables.		

Section Number & Title	Description of Change	Brief Rationale
	Removed stool sample rows from Table 5.1-9 through Table 5.1-12.	Removed to correct previous error and align with current biomarker schedules.

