3.4 Concomitant Treatments

3.4.1 Prohibited and/or Restricted Treatments

The following medications are prohibited during the study:

- Immunosuppressive agents (except to treat a drug-related adverse event)
- Systemic corticosteroids > 10 mg daily prednisone equivalent (except as stated in Section 3.4.3 or to treat a drug-related adverse event).
- Live/attenuated vaccines (eg, varicella, zoster, yellow fever, rotavirus, oral polio and measles, mumps, rubella [MMR])

• Any concurrent antineoplastic therapy (ie, chemotherapy, hormonal therapy, immunotherapy, radiation therapy except for palliative radiation therapy described in Section 3.4.3 or standard or investigational agents for treatment of cancer).

- Coronavirus disease 2019 (COVID-19) vaccines that are NOT live are permitted during the study and after the last dose of investigation product. Non-live COVID-19 vaccination is considered a simple concomitant medication within the study. However, the efficacy and safety of non-live vaccines (including non-live COVID-19 vaccines) in participants receiving study drug is unknown.
 - The following are NOT live vaccines: inactivated vaccines (eg, heat-killed and formalin-killed vaccines), subunit vaccines (eg, influenza and pneumococcal vaccines), toxoid vaccines, nucleic acid vaccines that do not encode potentially infectious virus (eg, Pfizer/BioNTech and Moderna COVID-19 vaccines) and replication-incompetent recombinant vector vaccines (eg, AstraZeneca/University of Oxford COVID-19 vaccine).
 - Please contact the Clinical Trial Physician/Medical Monitor with any questions related to COVID-19 vaccines.

Supportive care for disease-related symptoms may be offered to all subjects on the trial.

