3.4.3 Permitted Therapy

Subjects are permitted the use of topical, ocular, intra-articular, intranasal, and inhalational corticosteroids (with minimal systemic absorption). Adrenal replacement steroid doses including doses > 10 mg daily prednisone are permitted. A brief (less than 3 weeks) course of corticosteroids for prophylaxis (eg, contrast dye allergy) or for treatment of non-autoimmune conditions (eg, delayed-type hypersensitivity reaction caused by a contact allergen) is permitted.

The potential for overlapping toxicities with radiotherapy and nivolumab alone or in combination with either ipilimumab, BMS-986016, or daratumumab currently is not known. Therefore, palliative radiotherapy is not recommended while receiving study drugs. If palliative radiotherapy is required, then study drugs should be withheld for at least 1 week before, during, and 1 week after radiation. Subjects should be closely monitored for any potential toxicity during and after

receiving radiotherapy, and AEs considered related to radiotherapy should resolve to Grade ≤ 1 prior to resuming study drugs. Only non-target lesions included in the planned radiation field or CNS lesions may receive palliative radiotherapy. Details of palliative radiotherapy should be documented in the source records and electronic case report form (eCRF). Details in the source records should include: dates of treatment, anatomical site, dose administered and fractionation schedule, and adverse events. Subjects receiving limited field palliative radiation therapy will be considered to have unequivocal progression of disease in the non-target lesion. Symptoms requiring palliative radiotherapy should be evaluated for objective evidence of disease progression. Administration of additional study drugs to subjects who received limited field palliative radiation should follow guidelines specified in Section 4.3.8 Treatment beyond Disease Progression.

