Note: See for Section 3.1.4.1 for treatment duration

Nivolumab and Ipilimumab combination:

When both nivolumab and ipilimumab are to be administered on the same day, separate infusion bags and filters must be used for each infusion. Nivolumab is to be administered first. The nivolumab infusion must be promptly followed by a saline flush to clear the line of nivolumab before starting the ipilimumab infusion. The second infusion will always be ipilimumab and will start no sooner than 30 minutes after completion of the nivolumab infusion.

Dosing calculation based on weight:

The dosing calculations should be based on the body weight. If the subject's weight on the day of dosing differs by > 10% from the weight used to calculate the dose, the dose must be recalculated. The weight used to calculate the dose should always be the most recently recorded weight. All doses should be rounded to the nearest milligram. There will be no dose modifications allowed.

Body weight is determined as detailed in the Flow Chart/Time and Events Schedule of this protocol.

Dosing modifications:

There will be no dose modifications allowed for the management of toxicities of individual subjects.

For Q2W nivolumab dosing cycles, subjects may be dosed no less than 12 days between doses. For Q3W nivolumab dosing cycles, subjects may be dosed no less than 19 days between doses. For Q4W nivolumab dosing cycles, participants may be dosed no less than 25 days from the previous dose. For Q6W ipilimumab dosing cycles, participants may be dosed no less than 5 weeks from the previous dose. If dosing is delayed, both nivolumab and ipilimumab must be delayed together. If dosing is resumed after a delay, both nivolumab and ipilimumab must be resumed on the same day.

Table 4.3-5: Dosing Schedule for C5 Cohort: Nivolumab + BMS-986016 Combination		
Day 1 Week 1	Day 1, Week 3, 5, 7, 9 and every other week thereafter*	
240 mg nivolumab flat dose	240 mg nivolumab flat dose IV over 30 minutes	
160 mg BMS-986016	160 mg BMS986016 IV over 60 minutes	

Note: See for Section 3.1.4.1 for treatment duration

Table 4.3-6: Dosing Schedule for C6 Cohort: Nivolumab + Daratumumab Combination				
Drug	Dose	Frequency of administration	Route of administration	Duration
Nivolumab	240 mg flat dose	every 2 weeks starting on Week3	30 minute Intravenous (IV) infusion	Until progression, toxicity, or discontinuation from study

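### Section 4.3.8 can be read as allowing study drug during radiation therapy, inside the hold that Section 3.4.3 sets for safety

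*Combined protocol and SAP*

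**What the plan says.** - **Section 4.3.8** governs subjects who continue treatment after RECIST 1.1 progression. It lists five conditions, on clinical benefit, tolerance, performance status, urgent interventions and consent, and then adds: "Treatment beyond progression may be administered during or after localized interventions (surgery/radiation therapy". It also requires a documented discussion with the Medical Monitor and re-consent.
- **Section 3.4.1** prohibits concurrent antineoplastic therapy and includes in that list "radiation therapy except for palliative radiation therapy described in Section 3.4.3".
- **Section 3.4.3** discourages palliative radiotherapy on study drug and gives its reason: "The potential for overlapping toxicities with radiotherapy and nivolumab alone or in combination with either ipilimumab, BMS-986016, or daratumumab currently is not known". Its rule is: "If palliative radiotherapy is required, then study drugs should be withheld for at least 1 week before, during, and 1 week after radiation". On restarting it says: "AEs considered related to radiotherapy should resolve to Grade ≤ 1 prior to resuming study drugs".
- **Section 3.4.3** also counts limited-field palliative radiation as unequivocal progression of the non-target lesion and adds: "Administration of additional study drugs to subjects who received limited field palliative radiation should follow guidelines specified in Section 4.3.8 Treatment beyond Disease Progression".
- The **Summary of Key Changes for Protocol Amendment 09** explains the 4.3.8 sentence as: "Updated to clarify when treatment beyond progression may be administered".

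**The concern.** The hold in Section 3.4.3 is a safety rule, set because nobody yet knows how radiation toxicity combines with these drugs. A subject already treated beyond progression who then needs palliative radiation falls under both 3.4.3 and 4.3.8. A site that opens 4.3.8 for that subject finds a permission that covers radiation. It finds no hold, no recovery condition and no reference back to 3.4.3. The stated purpose of the sentence is to say when treatment may be given, so a site could reasonably take it as a dosing-time rule and infuse during the course or in the week on either side. Sites could also differ in what they do.

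**Working it through.** The plan gives no figure here to reproduce. The check compares the texts and then sizes the overlap.

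**1. The instructions side by side**

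| Question | 3.4.3 | 4.3.8 |
|---|---|---|
| Drug during radiation? | Should be withheld | May be administered |
| Drug in the week on either side? | Should be withheld | After: may be administered; before: not addressed |
| Recovery condition before restarting? | Radiotherapy-related AEs at Grade 1 or lower | None specific to radiation |
| Reference to the other section? | Yes, for subjects who have already been irradiated | None |

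Section 3.4.1 leaves no other kind of permitted radiation that would escape the hold. The pointer from 3.4.3 to 4.3.8 concerns subjects whose radiation is past, so it does not itself lead to dosing during a course. None of the five conditions in 4.3.8 concerns dose timing around radiation.

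**2. Length of the hold**

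Inputs: 7 days on each side (3.4.3, with the week before stated as a minimum) and a course length L of 1, 7 or 14 days (assumed).

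H = 7 + L + 7 = 15, 21 or 28 days.

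**3. Doses that fall due**

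Nominal nivolumab intervals T are 14, 21 and 28 days. Section 4.3 sets minimum intervals of 12, 19 and 25 days (for two-weekly dosing: "For Q2W nivolumab dosing cycles, subjects may be dosed no less than 12 days between doses"). In a window of W days, the number of doses lies between floor(W/T) and ceil(W/T), depending on when the window starts. For example, with T = 14 and H = 21, 21/14 = 1.5, which gives 1 to 2.

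| T (days) | Inside the course, L = 1 / 7 / 14 | Inside the hold, H = 15 / 21 / 28 |
|---|---|---|
| 14 (Q2W) | 0–1 / 0–1 / 1 | 1–2 / 1–2 / 2 |
| 12 (Q2W minimum) | 0–1 / 0–1 / 1–2 | 1–2 / 1–2 / 2–3 |
| 21 (Q3W) | 0–1 / 0–1 / 0–1 | 0–1 / 1 / 1–2 |
| 19 (Q3W minimum) | 0–1 / 0–1 / 0–1 | 0–1 / 1–2 / 1–2 |
| 28 (Q4W) | 0–1 / 0–1 / 0–1 | 0–1 / 0–1 / 1 |
| 25 (Q4W minimum) | 0–1 / 0–1 / 0–1 | 0–1 / 0–1 / 1–2 |

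Q2W applies to C3 initial treatment, C5, C6 in Weeks 3–24 and the safety cohort from Week 13. Q3W applies to Arm N+I in Weeks 1–12, the first four doses of cStage re-initiation and C3 re-initiation. Q4W applies to Arm N, Arm N+I from Week 13, C6 from Week 25, mStage re-initiation and later cStage re-initiation.

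**4. Longest gap if the hold is kept**

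The worst case is a dose due on the first day of the hold, so the gap since the last dose is T + H:

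- Q2W: 14 + 15, 21, 28 = 29, 35, 42 days
- Q3W: 21 + 15, 21, 28 = 36, 42, 49 days
- Q4W: 28 + 15, 21, 28 = 43, 49, 56 days

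Against the six-week limit (42 days), the worst case exceeds it on Q3W with a 14-day course and on Q4W with any of the three. Slow recovery from radiotherapy-related events would lengthen the gaps.

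**The case against.** The strongest reply is that the dose-timing reading of 4.3.8 is weak. The sentence puts surgery and radiation under the same *during or after*. Taken as dose timing, it would allow an infusion during an operation, which is implausible. *During* fits both interventions only if it means that the phase of treatment beyond progression may span them. That reading also keeps 3.4.3 effective: because 3.4.3 treats limited-field palliative radiation as progression, a 4.3.8 that lifted the hold would leave it little to govern. The hold has no exception for treatment beyond progression.

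There are safeguards too. The Medical Monitor must be consulted about continuing, and subjects are re-consented. Section 3.4.3 discourages radiation on drug, asks for close monitoring and limits it to non-target or CNS lesions.

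Much of this stands. A reader might infer that 4.3.8 orders the opposite of 3.4.3. It does not: it grants a permission, and withholding drug satisfies every section. But nothing in the documents states the phase reading. The verb is *administered*, and the stated rationale for the sentence fits either reading. The Medical Monitor discussion concerns the decision to continue and is not tied to dose timing around a later radiation course.

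A reader might also want to count weekly daratumumab (Cohort C6, Weeks 1–8), where the hold would cover 2 to 4 doses (15/7 to 28/7). That is an edge case. The first scheduled scan is at Week 6 ± 1 (Table 5.1-6), so few weekly doses remain for a subject already past progression. In Weeks 9–24 daratumumab is two-weekly, and a 28-day hold covers 28/14 = 2 nominal doses, below the three consecutive missed doses that trigger withdrawal or sponsor consultation in Section 4.3.3.

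**Conclusion.** The point holds as an unresolved ambiguity between current sections on a safety rule. Section 4.3.8 can be read as permitting a dose that 3.4.3 says should be withheld, and nothing elsewhere reconciles them. It should be fixed.

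Its reach is limited. It concerns radiation only, since 3.4.3 sets no hold for surgery, and mainly subjects already treated beyond progression who then need palliative radiation. That group is small and the documents do not count it. The dose counts rest on the assumed course of 1 to 14 days and measure scheduling overlap, not risk; the documents call the combined toxicity unknown and report no harm from it.

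A reader might infer that the primary result is at stake. The documents do not support that. Section 8.3.1 stops best overall response at the first documented progression or at subsequent therapy, and 4.3.8 dates progression to the initial event for subjects who continue. Doses given after that point do not enter the ORR.

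**What to change.** Replace the sentence in Section 4.3.8 with:

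> Treatment beyond progression may continue in subjects who undergo localized interventions (surgery/radiation therapy); for radiation therapy, study drugs should be withheld and resumed as specified in Section 3.4.3.

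This keeps the permission to continue and removes the reading that allows a dose during radiation. The wording uses *should*, to match 3.4.3. Writing *must* would make the rule stricter for these subjects than for everyone else.

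The cost is one sentence, with no new procedure or data. The downside is the interruption that 3.4.3 already specifies. Where the gap passes six weeks, Section 4.3.6 already allows continuation for non-drug-related reasons with approval from the Medical Monitor or designee. If the sponsor meant to relax the hold for these subjects, 3.4.3 should be revised instead, with a safety rationale that the documents do not now give.
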